Eligible subjects will be randomized 2:2:1:1 across 4 treatment groups in the DBT Phase: zavegepant 100 mg (n = 480); zavegepant 200 mg (n = 480); placebo matching zavegepant 100 mg (n = 240); or placebo matching zavegepant 200 mg (n = 240). Subjects will take the assigned study drug every day for 12 weeks. Subjects participating in PK draws will be required to dose in person at the study site to assess PK at the Week 4 and Week 8 Visits. Subjects will report migraine occurrence, migraine pain features and associated symptoms, and use of acute migraine medication in the eDiary during the DBT Phase. Upon completion of the DBT Phase, subjects may enter the 52-week OLE Phase and receive the assigned dose from the DBT Phase (either zavegepant 100 mg or 200 mg). If subjects do not enter the OLE Phase, they will have visits in the Follow-up Phase at approximately 2 weeks and 8 weeks after the last visit in the DBT Phase. Subjects who complete the OLE Phase or who discontinue early during the OLE Phase will also have visits in the Follow-up Phase at approximately 2 weeks and 8 weeks after the last visit in the OLE Phase.

[figure not shown]
Subjects will also report concomitant medication, including standard of care migraine medication (both prophylactic and acute), taken throughout the entire study in the concomitant medication paper diary.

STUDY SCHEMATIC

Observation, DBT, and Follow-up Phases

OLE and Follow-up Phases

Approximately 60 Weeks

TABLE OF CONTENTS

	IARY OF CHANGES	
CONFI	IDENTIALITY AND INVESTIGATOR STATEMENT	5
STUDY	Y SUMMARY (SYNOPSIS)	6
STUDY	Y SCHEMATIC	8
TABLE	E OF CONTENTS	9
LIST O	OF TABLES	12
	OF FIGURES	
LIST O	OF ABBREVIATIONS	13
1 IN'	TRODUCTION AND RATIONALE	15
1.1	BackgroundBackground	15
1.2	CGRP's Role in Migraine	16
1.3	Product Development Background	16
1.3.1	Clinical Experience	16
1.3.1.1	Single Ascending Dose (SAD) BHV3500-101	
1.3.1.2	Multiple Ascending Dose Study (MAD) BHV3500-102	
1.3.1.3	Phase 2/3 Dose Ranging Study (BHV3500-201)	17
1.3.1.4	BHV3500-103	
1.3.1.5	BHV3500-107	
1.3.2	Summary of Animal Data with Oral and Sublingual Zavegepant	17
1.4	Study Rationale	18
1.4.1	Study Design Rationale	18
1.4.2	Dose Selection Rationale	19
1.4.3	Other Rationale Related to the Compound / Study	19
1.4.4	Research Hypothesis	19
2 ST	UDY OBJECTIVES	20
2.1	Primary Objective(s)	20
2.2	Secondary Objective(s)	20
	Exploratory Objective(s)	
	UDY ENDPOINTS	
	Primary Endpoint(s)	
	Secondary Endpoint(s)	
	Definition of Migraine Days	

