4.3.3 Open-label Extension (OLE) Phase

The OLE Phase will be up to 52 weeks through the Week 64 or EOT Visit.

Note that the OLE Phase was added to the study design after some subjects already entered the Follow-up Phase after the DBT Phase. *Subjects who complete 12 weeks of the DBT Phase and have not entered the Follow-up Phase* may be offered to enter the OLE Phase. Subjects must meet the same laboratory eligibility criteria assessed prior to randomization in

the DBT Phase in order to be eligible for the OLE Phase. Repeat labs will not be allowed at the week 12 visit to determine OLE eligibility. The DBT Week 12 laboratory results will be used to assess eligibility for the OLE Phase. Once the Week 12 laboratory results are received and eligibility is confirmed, the subject should be contacted by telephone and instructed to start taking open-label study drug.

Subjects who (1) discontinue early from the DBT Phase or (2) have already entered the Follow-up Phase are not eligibile to enter the OLE Phase.

Eligible subjects will have study visits approximately every 2 weeks during the first month of the OLE Phase and then every 4 weeks, through Week 64. See Table 2 for schedule of procedures.

Subjects randomized to zavegepant 100 mg or matching placebo in the DBT Phase will receive open-label zavegepant 100 mg in the OLE Phase. Subjects randomized to zavegepant 200 mg or matching placebo in the DBT Phase will receive open-label zavegepant 200 mg in the OLE Phase.

At each visit, the study drug wallet will be reviewed for compliance and concomitant medication use will be reviewed (and compared to concomitant medication paper diary entries, where applicable). Subjects will be dispensed additional study drug as needed. Additional safety assessments (including laboratory tests and ECGs) will be performed per the schedule outlined in Table 2.

Subjects will not use the eDiary in the OLE Phase.

Subjects must continue to record use of concomitant medications in the concomitant medication paper diary through the entire OLE Phase.

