Safety Endpoint	Number and percentage of subjects with AEs by intensity, serious adverse events (SAEs), AEs leading to study drug discontinuation, and grade 3 to 4 laboratory test abnormalities on treatment
Summary	Frequency by treatment group for the DBT and OL zavegepant safety analysis sets
Intercurrent Events	Study drug discontinuation: while-on-treatment strategy
	Non-study prophylactic migraine medication use: treatment policy strategy
	Nonstudy acute migraine-specific medication use: treatment policy strategy
	Use of nonstudy other medication to treat headache (migraine or nonmigraine) or aura: treatment policy strategy
Objective 8	Frequency of ALT or AST > 3x upper limit of normal (ULN) concurrent with TBL > 2x ULN in subjects treated with zavegepant during the DBT and OLE Phases
Safety Endpoint	Number and percentage of subjects with AST or ALT elevations $> 3x$ ULN concurrent (i.e., on the same laboratory collection date) with TBL $> 2x$ ULN on treatment
Summary	Frequency by treatment group for the DBT and OL zavegepant safety analysis sets with LFT data
Intercurrent Events	Study drug discontinuation: while-on-treatment strategy
	Non-study prophylactic migraine medication use: treatment policy strategy Nonstudy acute migraine-specific medication use: treatment policy strategy
	Use of nonstudy other medication to treat headache (migraine or nonmigraine) or aura: treatment policy strategy
Objective 9	Frequencies of hepatic-related AEs and hepatic-related AEs leading to study drug discontinuation in subjects treated with zavegepant during the DBT and OLE Phases
Safety Endpoint	Number and percentage of subjects with hepatic-related AEs and hepatic-related AEs leading to study drug discontinuation on treatment
Summary	Frequency by treatment group for the DBT and OL zavegepant safety analysis sets

Intercurrent Events Study drug discontinuation: while-on-treatment strategy

Non-study prophylactic migraine medication use: treatment policy strategy Nonstudy acute migraine-specific medication use: treatment policy strategy

Use of nonstudy other medication to treat headache (migraine or nonmigraine) or aura:

treatment policy strategy

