## 4.2 Treatment Groups

Treatment groups in the DBT Phase are zavegepant 100 mg, zavegepant 200 mg, placebo 100 mg, and placebo 200 mg. OL zavegepant dose groups in the OLE Phase are zavegepant 100 mg and zavegepant 200 mg.

The safety analysis sets are assessed by as-treated treatment group (i.e., actual treatment received), the randomized, full, efficacy, and migraine analysis sets are assessed by as-randomized treatment group, and the enrolled analysis set is assessed overall.

If a subject takes  $\geq 1$  dose of planned randomized DB study drug, then that subject is considered to have as-treated treatment group equal to as-randomized treatment group (see Section 6.2.6.2).

If there are non-randomized subjects who take study drug, then the as-randomized treatment group of "not randomized" is included in the full analysis set augmented with the safety analysis set.

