#### 6.1.1.1 Tables

Treatment group presentation in tables by analysis set is shown in Table 4. Exceptions are specified in subsequent sections as needed.

Table 4 Treatment Group Presentation in Tables by Analysis Set

Analysis Set	Number of Columns	Abbreviated Treatment Group
Enrolled	1	Overall
Full, DBT efficacy, migraine, DBT safety, interim safety by treatment group, {zavegepant pooled}, {placebo pooled}, and {overall}	4 to 7	ZAV 100 mg ZAV 200 mg {ZAV Pooled} PBO 100 mg PBO 200 mg {PBO Pooled}
OL zavegepant safety by OL zavegepant dose and overall	3	{Overall} OL ZAV 100 mg OL ZAV 200 mg Overall
DB or OL zavegepant safety by DB or OL zavegepant dose and overall	3	DB ZAV or PBO 100 mg/OL ZAV 100 mg DB ZAV or PBO 200 mg/OL ZAV 200 mg Overall
Follow-up safety by treatment group/OL zavegepant status and overall	6	DB ZAV 100 mg/OL ZAV 100 mg DB ZAV 200 mg/OL ZAV 200 mg DB PBO 100 mg to OL ZAV 100 mg DB PBO 200 mg to OL ZAV 200 mg DB PBO Pooled No OL ZAV Overall

"ZAV Pooled" is defined as the DB zavegepant 100 mg and DB zavegepant 200 mg treatment groups combined. "PBO Pooled" is defined as the DB placebo 100 mg and DB placebo 200 mg treatment groups combined. "DB PBO X mg to OL ZAV X mg" denotes as-treated DB placebo X mg subjects in the OL zavegepant safety analysis set (X = 100 or 200), and "DB PBO Pooled No OL ZAV" denotes as-treated DB placebo pooled subjects not in the OL zavegepant safety analysis set; note that these 3 placebo groups add to the "PBO Pooled" group.

Results for study population also include overall treatment group (see Sections 6.2 and 6.4).

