#### 6.2.3.3 Subject Disposition during the DBT Phase

The frequency table of subject disposition during the DBT Phase is provided for the DBT safety analysis set by as-treated treatment group, zavegepant pooled, placebo pooled, and overall based on the DB Subject Status CRF, and displays the following categories:

- Ongoing in the DBT Phase. These are identified as subjects with (1) missing response to the question "Did the subject complete the DBT Phase?" and (2) missing DB study drug last date. This category only exists before the LSLV database lock. After the LSLV database lock, subjects with missing response are categorized as "Did not complete the DBT Phase".
- Completed the DBT Phase. These are identified as subjects with (1) "yes" response to the question "Did the subject complete the DBT Phase?" and (2) nonmissing DB study drug last date.
- Did not complete the DBT Phase. These are identified as subjects with (1) "no" or missing response to the question "Did the subject complete the DBT Phase?" and (2) nonmissing DB study drug last date.
  - o Reasons for not completing the DBT Phase, including not reported
- Continued to the next phase. These are identified as subjects with (1) "yes" response to the question "Is the subject continuing to the Follow-up Phase?" and missing response to the question "Is the subject continuing to the next phase?", or (2) "yes" response to the question "Is the subject continuing to the next phase?".
  - Next phase, i.e., OLE or Follow-up. The next phase is determined from the response to the "If Yes, select the next phase" question, if available. Otherwise, if there is a "yes" response to the question "Is the subject continuing to the Follow-up Phase?", then the next phase is considered to be Follow-up.
- Did not continue to the next phase. These are identified as subjects with (1) missing response to the question "Is the subject continuing to the next phase?" and "no" response to the question "Is the subject continuing to the Follow-up Phase?", or (2) "no" response to the question "Is the subject continuing to the next phase?", or (3) after the LSLV database lock, missing responses to both questions about continuing.
  - Reasons for not continuing to the next phase, including not reported. These are based on reasons for not continuing to the Follow-up Phase or the next phase.

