## 6.4 Safety

Safety parameters include the following: deaths; AEs; laboratory tests; vital signs; physical measurements; electrocardiograms (ECGs); and Columbia-Suicidality Severity Rating Scale (C-SSRS.

Tables of safety endpoints are provided according to safety analysis period and analysis set as follows:

- On-DBT for the DBT safety analysis set by treatment group, zavegepant pooled, and placebo pooled
- Post-DBT pre-OL zavegepant for the interim safety analysis set by treatment group, zavegepant pooled, placebo pooled, and overall
- On-OL zavegepant for the OL zavegepant safety analysis set by OL zavegepant dose and overall
- On-DB or OL zavegepant for the DB or OL zavegepant safety analysis set by DB or OL zavegepant dose and overall
- Follow-up for the follow-up safety analysis set by treatment group/OL zavegepant status and overall.

Treatment group is as-treated according to Section 6.1.1.1.

Measurements are slotted into analysis periods and analysis visits using the following steps:

- 1) Measurements are slotted into the pretreatment, on-treatment safety, and follow-up safety analysis periods.
- 2) Measurements are slotted into analysis visits in the analysis periods listed in the previous step (see Table 5). This does not apply to AEs.
- 3) Measurements in the on-treatment safety analysis period are slotted further into the on-DBT, post-DBT pre-OL zavegepant, and on-OL zavegepant safety analysis periods.

Refer also to the Core SAP for details about measurement slotting. See Sections 6.2.5, 7.2 and 7.3 for definitions of baseline, analysis periods, and analysis visit windows, respectively.

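### On-open-label AE, hepatic AE and LFT-elevation frequencies are tabulated by open-label dose only, so continuing zavegepant subjects and former placebo subjects starting the drug share each column

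*SAP*

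**What the plan says.** For the open-label period, SAP 6.4 specifies "On-OL zavegepant for the OL zavegepant safety analysis set by OL zavegepant dose and overall". Table 4 in SAP 6.1.1.1 has the matching row, "OL zavegepant safety by OL zavegepant dose and overall", with three columns: OL 100 mg, OL 200 mg and overall. The AE overview (6.4.1.2), the on-OL AE tables including the hepatic AEs (6.4.1.4) and the LFT-elevation tables (6.4.2.2) use this set and state no further split.

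Protocol 4.3.3 determines who is in a dose column: "Subjects randomized to zavegepant 100 mg or matching placebo in the DBT Phase will receive open-label zavegepant 100 mg in the OLE Phase". The 200 mg rule is parallel. Entry requires the pre-randomization laboratory limits to be met on the Week 12 sample. Those limits exclude bilirubin above 1x ULN and AST or ALT at or above 1x ULN (Protocol 5.3, items 5f and 5g). In addition, "Repeat labs will not be allowed at the week 12 visit to determine OLE eligibility".

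SAP Table 2 gives the summary for secondary objective 8 as "Frequency by treatment group for the DBT and OL zavegepant safety analysis sets with LFT data". Objectives 7 and 9 are worded the same way apart from the LFT-data restriction. SAP 4.2 names the four DB arms as the treatment groups and then adds that "OL zavegepant dose groups in the OLE Phase are zavegepant 100 mg and zavegepant 200 mg".

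**The concern.** Secondary objectives 7 to 9 ask for AE, liver-test and hepatic AE frequencies during the OLE as well as the DBT Phase. The two groups in a dose column arrive differently. A former zavegepant subject has completed 12 weeks on drug and passed a check, on drug, of the same liver tests that objective 8 counts. A former placebo subject passes the same check before any exposure. A hepatic or tolerability effect concentrated in early exposure would show mainly in the second group, and one that builds with duration mainly in the first. A single pooled frequency cannot show which has happened, and no planned frequency table of the on-OL period separates the two.

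**Working it through.** The plan states no open-label hepatic rate, so there is no such figure to reproduce. The check covers the make-up of a column and what pooling does to a frequency.

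Inputs:
- Allocation: "Eligible subjects will be randomized 2:2:1:1 across 4 treatment groups in the DBT Phase" (Protocol synopsis), planned as 480, 480, 240 and 240, so 2 zavegepant to 1 placebo within each dose.
- OLE entrants: about 1200 of 1440 (Protocol 5.1), or 1200/1440 = 83.3%.
- LFT-table confidence level: 97.5% (SAP 6.4.2.2).

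**Make-up of a column.** With equal entry rates, each OL dose has 1200/2 = 600 subjects: 600 x 2/3 = 400 former zavegepant and 600 x 1/3 = 200 former placebo. Two assumed departures that keep the total at 1200:
- Entry of 75% (zavegepant) and 100% (placebo): 480 x 0.75 = 360 and 240 x 1.00 = 240, a placebo-origin share of 240/600 = 40%.
- Entry of 95% and 60%: 480 x 0.95 = 456 and 240 x 0.60 = 144, a share of 144/600 = 24%.

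**Effect of pooling.** Pooled frequency = (400 x continuer rate + 200 x new-starter rate)/600. All rates below are illustrations:

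| Continuers | New starters | Events | Pooled |
|---|---|---|---|
| 0.5% | 2.0% | 2 + 4 = 6 | 1.0% |
| 0.5% | 1.0% | 2 + 2 = 4 | 0.67% |
| 0.1% | 2.0% | 0.4 + 4 = 4.4 | 0.73% |
| 1.0% | 1.0% | 4 + 2 = 6 | 1.0% |

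In the first row the new-starter rate is halved and the continuer rate doubled. In the last row nothing is distorted. With the first row's rates, a placebo-origin share of 24% gives 0.24 x 2.0% + 0.76 x 0.5% = 0.86%, and 40% gives 0.40 x 2.0% + 0.60 x 0.5% = 1.10%.

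**Zero events.** The exact two-sided 97.5% upper limit is 1 - 0.0125^(1/n). The exact method is an assumption; SAP 6.4.2.2 does not name one. It gives 0.73% for n = 600, 1.09% for n = 400 and 2.17% for n = 200. A pooled 0/600 therefore looks about three times as reassuring (2.17/0.73 = 3.0) as the 200 new starters alone could support.

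**Maximum exposure.** The table aligned to first zavegepant dose follows former zavegepant subjects for up to 12 + 52 = 64 weeks and former placebo subjects for up to 52.

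**The case against.** The case for leaving the tables alone has real content.

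- *Origin is not lost everywhere.* A reader might infer that all on-OL safety results are by dose only. That is not so: changes in laboratory tests, vital signs and ECG at open-label visits are tabulated by DB treatment group (SAP 6.4.2.3, 6.4.3.1, 6.4.4.1). These are values and changes, however, not the event frequencies that objectives 7 to 9 request.
- *First exposure is covered elsewhere.* On-DBT tables show the first 12 weeks by arm against concurrent placebo, with 480 + 480 = 960 zavegepant subjects planned. The AE overview and LFT table for DB or OL zavegepant start at each subject's first zavegepant dose (SAP 7.1). This stands as partial mitigation. Those latter tables still merge origins, with unequal maximum exposure.
- *SAP Table 2 may not contradict Table 4.* It is tempting to read "Frequency by treatment group for the DBT and OL zavegepant safety analysis sets with LFT data" as demanding the four DB arms. But Table 4 labels its OL dose columns as treatment groups, and SAP 4.2 places the OL dose groups under that heading. The wording is ambiguous, so a contradiction is not established.
- *The Week 12 laboratory check is not specific to zavegepant subjects.* Every OLE entrant passes it. The difference is only that one group does so on drug.
- *Exclusions are not wholly hidden.* SAP 6.2.3.3 shows, by arm, DBT completers and "Next phase, i.e., OLE or Follow-up", so completers not entering the OLE can be found by subtraction. That number does not isolate laboratory failures, because the OLE was added after some subjects had already entered Follow-up (Protocol 4.3.3).
- *Individual cases remain traceable.* Listings show the randomized arm and, for placebo subjects, zavegepant study day (SAP 6.1.1.2). With few events, a reader could attribute them by hand.
- *Output was deliberately reduced* after termination for business reasons (SAP 1), and Protocol 9.3.2 promises only descriptive frequencies for the three safety sets. This argues for a small addition rather than a full second set of tables.

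**Conclusion.** The point holds as a cheap improvement to descriptive OLE safety reporting, not as an error in the plan. On-OL AE, hepatic AE and LFT-elevation frequencies are weighted averages of continuers and new starters, about 2:1 at planned size with equal entry, and the plan has no frequency table that separates them. Whether this misleads depends on the two rates differing. A reader might conclude that the pooled rate understates first-exposure risk, or describes neither group. The documents do not support that unconditionally, since they give no open-label rates and equal rates produce no distortion. The group sizes are planning figures; the study was terminated in December 2023 (SAP 1), so actual columns may be smaller. Power, the efficacy analyses and the OLE entry rule are unaffected.

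**What to change.** 1. In Table 4 and SAP 6.4, keep the pooled OL dose and overall columns and add two origin columns within each dose: DB zavegepant to OL zavegepant, and DB placebo to OL zavegepant. Apply them to the on-OL AE overview, hepatic AE and LFT-elevation tables. Table 4's follow-up row already carries labels of this kind. The note below the table defines the placebo-origin groups; the zavegepant-origin columns should be restricted explicitly to the OL safety set.
2. Reword the summary rows for secondary objectives 7 to 9 in SAP Table 2, and for exploratory objectives 8 and 9 in Table 3, so that they name the grouping used for the OL set in Table 4.
3. Optionally, add to SAP 6.2.3.3 the number, by DB arm, of DBT completers not entering the OLE whose Week 12 ALT, AST or bilirubin was outside the entry limits.

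The cost is SAP wording and a few more columns in retained tables. The statistical price is a smaller denominator in each origin column, hence the wider limits shown above; keeping the pooled columns preserves the dose-level summary. No trial procedure changes.

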#### 6.4.1 Adverse Events

Refer to the Core SAP for the following: AE start and end date imputation; death date derivation; rules for counting and rounding in AE frequency tables; definitions of AEs related to study drug, and AEs of special interest; and TLF contents.

Frequency tables of AEs by SOC and PT display AEs in descending order of overall frequency within SOC and PT, unless otherwise specified.

The by-subject listing of AEs (i.e., non-SAEs and SAEs) is provided for the enrolled analysis set.

#### 6.4.1.1 Deaths

Deaths are identified from any of the following sources:

- AE CRF with any of the following: PT or reported term of "death"; outcome of fatal; "yes" response to any death-related question (e.g., "Did the AE result in death?"; "Is a death certificate available?"; "Is an autopsy report available?"); complete or partially complete death date
- DB Subject Status CRF with any of the following: death as reason for DBT Phase non-completion; death as reason for not continuing to the next phase (see Section 6.2.3.3)
- OLE Subject Status CRF with any of the following: death as reason for OLE Phase non-completion; death as reason for not continuing to the Follow-up Phase (see Section 6.2.3.4)
- Follow-up Subject Status CRF: death as reason for Follow-up Phase non-completion (see Section 6.2.3.5).

The by-subject listing of deaths is provided for the enrolled analysis set.

#### 6.4.1.2 AE Overviews

An AE overview frequency table displays the following categories without SOC and PT: any AE; AE related to study drug; AE leading to study drug discontinuation; SAE; SAE related to study drug; medication-overuse headache AE; hepatic-related AE; hepatic-related AE leading to study drug discontinuation; potential drug abuse AE; cardiovascular AE; and suicidality AE.

AE overview frequency tables are produced for the following safety analysis periods and analysis sets:

- On-DBT for the DBT safety analysis set
- Post-DBT pre-OL zavegepant for the interim safety analysis set
- On-OL zavegepant for the OL zavegepant safety analysis set
- On-DB or OL zavegepant for the DB or OL zavegepant safety analysis set
- Follow-up for the follow-up safety analysis set.

